3.8 OFF STUDY CRITERIA

3.8.1 Patients may be taken off study for the following non-medical or administrative reasons:

- Patient refuses the procedure or further treatment
- It is deemed in the patient’s best interest as determined by the PI.
- Serious protocol violation as determined by the PI.

3.8.2 *Development of a concurrent serious medical condition that precludes the completion of fiducial marker placement, radiation therapy or follow-up.*

3.8.3 *Tumor progression (if occurs during treatment, at the end of radiation therapy unless the completion of local therapy is not indicated)*

3.8.4 *Initiation of cytotoxic chemotherapy (if occurs during treatment, at the end of radiation therapy unless the completion of local therapy is not indicated)*

3.8.5 *Development of a concurrent serious medical condition during active treatment and not attributable to therapy that precludes the completion of active treatment.*

3.8.6 *The completion of 36 months (3 years) follow-up.*

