3.1.3 Criteria for Dose Escalation

Each dose cohort will accrue 3 patients. If there are no DLT in 3 patients then 3 patients will be accrued to the next dose level. If two or more patients experience a DLT then the MTD will be exceeded and the prior lower dose cohort will be considered the MTD. If a DLT occurs in one of three patients then an additional 3 patients will be accrued to that dose level. If fewer than 2 of 6 patients experience an acute DLT in the expanded cohort then patients will be accrued to the next dose cohort. If 2 or more of 6 patients experience a DLT then the MTD will be exceeded and the prior, lower dose cohort will be considered the MTD.

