3.1.4 Definition of Dose Limiting Toxicity (DLT)

An acute DLT will be defined as RTOG grade 3 or greater, acute GI or GU toxicity (see appendix IIA) within 3 months after the completion of radiation. Thus, accrual to an escalated dose cohort may need to be delayed so that all 3 patients in the current cohort are followed for 2 months. Given that the volume of normal tissue irradiated to standard dose or higher will be substantially limited, late toxicity is less of a concern than acute toxicity.

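### A patient can go off study before the DLT window closes, and the plan does not say whether that patient still counts among the 3 or 6 who decide escalation

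*Combined protocol and SAP*

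**What the plan says.** **Leaving the study.** Section 3.8.4 gives as an off-study criterion "Initiation of cytotoxic chemotherapy (if occurs during treatment, at the end of radiation therapy unless the completion of local therapy is not indicated"), and 3.8.3 uses the same timing for tumor progression. Section 3.8.1 permits removal for administrative reasons, among them "Patient refuses the procedure or further treatment". Sections 3.8.2 and 3.8.5 cover a concurrent serious condition. When a patient leaves, 3.9 asks for the reason and an off-study form.

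**The endpoint.** Section 3.1.4 defines a DLT as acute RTOG GI or GU toxicity of grade 3 or more "within 3 months after the completion of radiation". It adds that "accrual to an escalated dose cohort may need to be delayed so that all 3 patients in the current cohort are followed for 2 months". RTOG grading is weekly during treatment and at its completion (3.4.3), then at 2, 4, 8 and 12 weeks (3.4.4).

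**The decision rule.** Section 3.1.3 says "Each dose cohort will accrue 3 patients". It continues: "If there are no DLT in 3 patients then 3 patients will be accrued to the next dose level", and "If a DLT occurs in one of three patients then an additional 3 patients will be accrued to that dose level". After expansion, escalation requires fewer than 2 DLTs in 6. The section does not define an evaluable patient and does not mention replacement.

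**Operating characteristics.** Section 5.4 gives escalation probabilities of 0.91, 0.49, 0.17 and 0.03 at true DLT probabilities of 0.1, 0.3, 0.5 and 0.7, and caps accrual at 19.

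**The concern.** A patient who progresses or starts chemotherapy during treatment is off study at the end of radiation, just as the 3-month post-radiation period begins. If either happens after radiation, nothing defers the exit, and the patient can leave in the middle of the window. Refusal or a concurrent condition can end observation earlier still, possibly before the cohort's nodal dose has been delivered.

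Nothing in the plan restores the lost observation. Section 3.9 does not ask for it, the visits in 3.4.4 carry no instruction to continue after off-study, and adverse event reporting under 7.3.1 stops 30 days after the last dose. The MTD is decided on 3 or 6 patients, so the handling of one incomplete patient can change a cohort's decision. Refusal of further treatment may also be related to toxicity, in which case the missing information would not be missing at random.

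**Working it through.** **Inputs.** The rule is from 3.1.3 and the stated probabilities from 5.4. The documents give no rate of early departure and no share of DLT risk falling after a departure, so both are assumptions here.

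**Step 1: reproduce the plan's figures.** With p the true DLT probability and q = 1 − p, and all patients fully observed:

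P(escalate) = q³ + 3pq² × q³

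- p = 0.1: 0.729 + 0.243 × 0.729 = 0.906
- p = 0.3: 0.343 + 0.441 × 0.343 = 0.494
- p = 0.5: 0.125 + 0.375 × 0.125 = 0.172
- p = 0.7: 0.027 + 0.189 × 0.027 = 0.032

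These match 5.4. The shorter rule in the précis (escalate on fewer than 2 of 3, no expansion) gives 0.972, 0.784, 0.500 and 0.216 and does not match. The stated figures therefore belong to 3.1.3 with complete observation.

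**Step 2: one of the first 3 leaves early.** Let g be the share of that patient's DLT risk that goes unobserved, so that the observed DLT probability is r = p(1 − g). The patient is counted DLT-free unless a DLT was seen before leaving, and any expansion patients are complete:

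P(escalate) = q²(1 − r) + [q²r + 2pq(1 − r)] × q³

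Worked at p = 0.5:

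- g = 0.5, r = 0.25: 0.25 × 0.75 + [0.0625 + 0.375] × 0.125 = 0.1875 + 0.0547 = 0.242
- g = 1, r = 0: 0.25 + 0.5 × 0.125 = 0.3125

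| True DLT probability | Fully observed | Half the risk observed | None observed |
|---|---|---|---|
| 0.3 | 0.494 | 0.564 | 0.634 |
| 0.5 | 0.172 | 0.242 | 0.312 |
| 0.7 | 0.032 | 0.067 | 0.101 |

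**Step 3: dropping the patient instead.** Suppose an unobserved patient is removed without replacement: 0 of 2 escalates, 1 of 2 adds 3, and fewer than 2 of 5 escalates. The probability is q² + 2pq × q³, the same expression as g = 1. Dropping the patient does not restore the design.

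**Step 4: averaged over a departure rate.** Step 2 takes one departure as given. If instead each patient leaves early with probability d, a share f of a leaver's risk is unobserved, and leavers are counted DLT-free, replace p in step 1 by p(1 − d·f). With f = 1 and p = 0.5, escalation is 0.202 at d = 5%, 0.234 at 10% and 0.309 at 20%. With f = 0.5 and d = 5% it is 0.186. The chance that at least one of 3 leaves is 1 − (1 − d)³: 0.143, 0.271 and 0.488 at these three rates.

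**Step 5: room for replacements.** The cap of 19 equals 10 + 3 × 3. If all three cohorts fill, no place is left for a replacement. The expansions that 3.1.3 allows would by themselves need up to 10 + 3 × 6 = 28.

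**The case against.** A reader might infer that the plan scores unobserved patients as DLT-free and is therefore biased toward escalation. The documents do not support that. Section 3.1.3 is silent on early departures, and 3.1.4 contemplates following the whole cohort before escalating. Under 7.5.1 the team discusses each patient weekly and bases dose decisions on toxicity data. It could replace or exclude a leaver, or score the leaver as a DLT, which would move the probability the other way. This part of the objection stands: the defect is undefined handling, not a stated scoring rule.

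The exits may also be few and only partly blind. Section 3.8.1 is permissive, and 3.8.5 is limited to conditions not due to therapy. Recurrence under 5.2 needs three consecutive PSA rises after treatment, which the visit schedule could hardly show before week 8 to 12. Weekly grading means that a patient who leaves at the last fraction has been graded throughout the course. This also stands, and it makes the none-observed column a worst case. How much risk is lost depends partly on whether the DLT window includes the treatment period, which 3.1.4 leaves unclear.

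The objection does not close the gap. The follow-up sentence in 3.1.4 is conditional, names 2 months against a 3-month window, refers to 3 patients and not an expanded 6, and does not say what happens when a patient cannot be followed. Meanwhile 3.8.3 and 3.8.4, applied as written, end study participation when post-radiation observation should begin.

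**Conclusion.** The point holds as an omission with a stated cause. The off-study rules can end observation before the DLT window closes, and no rule says how such a patient enters the count of 3 or 6. The probabilities in 5.4 are correct for 3.1.3 but apply only when every counted patient is fully observed.

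If one of the first 3 leaves early and is counted DLT-free or dropped without replacement, escalation at a true DLT probability of 0.5 rises from 0.17 to 0.24 with half the risk observed and to 0.31 at worst. The corresponding changes are 0.49 to 0.56 or 0.63 at a DLT probability of 0.3, and 0.03 to 0.07 or 0.10 at 0.7. These sizes depend on an assumed departure and an assumed scoring convention, neither of which is in the documents. With low departure rates the average effect is small, but for a cohort in which a departure occurs it is not.

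**What to change.** - **Section 3.8:** state that patients who go off treatment, progress or start chemotherapy continue RTOG acute GI/GU grading at the existing 2, 4, 8 and 12-week visits unless they withdraw consent. Say how an event after the start of chemotherapy is attributed, since 3.1.5 ties the MTD to DLTs attributed to radiation.
- **Section 3.1.3:** apply the rule to DLT-evaluable patients, meaning any patient with a DLT, or one who received the assigned nodal course and completed the DLT window. Replace the others before the cohort decision, and report each with the reason for leaving and the highest grade seen. Replacement preserves the stated probabilities only if leaving is unrelated to DLT risk, so continued follow-up comes first.
- **Section 3.1.4:** reconcile the 2-month and 3-month periods, and state whether toxicity during treatment counts.
- **Section 5.4:** revise the 19-patient cap so that it can hold replacements and the expansions already allowed.

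The cost is a short amendment to four sections, an occasional replacement patient, and a short delay to that cohort's decision. No new visits are needed.

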3.9 POST-STUDY EVALUATION

- At the time a patient comes off study the reason for withdrawal should be documented.
- The patient should be registered off- protocol by completing the Off Study/ Death Notification Form available from the web site (<http://home.ccr.cancer.gov/intra/eligibility/welcome.htm>) and faxing it to the Central Registration Office at [contact].

4.0 SUPPORTIVE CARE

These procedures may require supportive care including nursing care, local anesthetic, analgesics, anti-emetics, and antibiotic prophylaxis. Please refer to section 3.2.2.2 – 3.2.2.3 for details. In the event that a patient has a reaction (allergic) to the contrast agent or medications, all appropriate medical measures will be taken.

The most common acute side effects of radiation therapy for prostate cancer, urethritis, cystitis and proctitis, may be treated with medications consistent with the standard of practice in the radiation oncology community. It is anticipated that a minority of patients may require short-term in-patient care for problems related to this protocol, namely an inability to void immediately post-op. In such circumstances, patients will be admitted to the Clinical Center under the care of the Urologic Oncologist. Medications should be listed in the patient's records.

5.0 DATA COLLECTION AND EVALUATION

5.1 DATA COLLECTION

- Clinical data and acquired samples/images will be recorded in a NCI CCR database (C3D).
- Clinical data collection will include: demographic information, pathologic diagnosis, clinical stage, PSA values, history including concurrent therapies, time of biopsy, locations of biopsies, pathology reports of biopsies, dose of radiation delivered, and toxicity assessment.
- Tissue experiments to be performed are pilot and preliminary in nature. Data from assays run at the NIH will be collected in laboratory notebooks, and the NCI online microarray database.
- MRSI and dynamic MRI measurement along with corresponding sites of tissue acquisition will be digitally archived and processed using computer software in the Radiology department of the Clinical Center, NIH, and the Radiation Oncology Branch, NCI.

End of study procedures: Data will be stored according to HHS, FDA regulations, and NIH Intramural Records Retention Schedule as applicable.

Loss or destruction of data: Should we become aware that a major breach in our plan to protect subject confidentiality and trial data has occurred, the IRB will be notified.

5.2 RESPONSE CRITERIA

Response of tumor will be determined by tracking serum PSA levels. Three consecutive rises of the PSA post-treatment will define disease recurrence. The time of disease recurrence will be back dated to the first rise in PSA. This methodology is as prescribed by the American Society of Therapeutic Radiation Oncology (ASTRO.)

5.3 TOXICITY CRITERIA

- Acute toxicities will be evaluated by the CTC, Version 3.0. (<http://ctep.info.nih.gov>).
- We will also utilize the RTOG acute and Late toxicity GI/ GU scales as in appendices II A & B.

5.4 STATISTICAL SECTION

This is a phase I study to determine the maximum tolerated dose (MTD) with MRI-guided radiation dose escalation to regions of interest within the prostate gland. The dose cohorts and MTD are defined in Section 3.1.1. With this design, the probabilities of dose escalation are 0.91, 0.49, 0.17, and 0.03 if the probabilities of a DLT are 0.1, 0.3, 0.5, and 0.7, respectively

Secondary analysis includes evaluating the frequency of late term toxicities. We will tabulate the frequency of late term toxicities. All secondary analyses will be reported as exploratory.

The maximum number of patients accrued to this trial will be 19 patients. We anticipate accruing these patients within 2 years.

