- On the first 10 patients, we will perform approximately 5 CT simulations throughout the course of their therapy. On each simulation, the initial treatment plan will be re-run. The dose-volume data from target and normal tissues will then be re-analyzed. From this analysis we will be better able to determine the size of margins needed to account for organ motion and changes such as varying amounts of gas in the bowel and fluid in the bladder. To the best of our knowledge, no such analyses have been published.
- If the initial part of this trial is feasible, we will proceed to a phase I dose escalation trial of radiation to the at-risk lymph nodes. The primary statistical objective of the phase I portion of this study is to estimate the Maximum Tolerated Dose (MTD) of external beam radiation based on evaluating acute toxicity. The study will be conducted with a dose-escalation design with 3 patients in each dose cohort. If fewer than 2 of 3 patients experience an acute DLT than patients will be accrued to the next dose cohort. If 2 or more of 3 patients experience a DLT then the MTD will be exceeded and the prior, lower dose cohort will be considered the MTD. Secondary objectives of this study are to relate patterns in gene and protein expression to response and toxicity and to evaluate the frequency of late term toxicity.
- Specific procedures and risks will be described in a separate consent to be obtained at the time of biopsy. Tissue samples will be processed for cDNA microarray testing and stored for future analysis in the Radiation Oncology Branch, NCI.
- Anatomic Magnetic Resonance Imaging (MRI) and MR biological images of the prostate and pelvis will be obtained and tissue will be acquired with biopsy locations precisely translated (co-registered) to an MR image of reference. A fiducial marker (gold seed) will be left at the biopsy site as a fiducial marker to direct future radiation therapy to the prostate. If necessary, additional fiducial markers will be placed for prostate localization during treatment.

SCHEMA

Pathologic Diagnosis of Prostate Cancer

REGISTER:

Patients who require whole pelvis radiation therapy.

INELIGIBLE
Those who require radiation therapy to the prostate gland alone.

Perform MRI guided biopsies of areas suspicious for cancer. Leave fiducial markers at these locations.

Treatment

First 10 Patients (Feasibility Testing Period)

- The MRI of the prostate and pelvis will be registered to the treatment planning CT scan.

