3.0 STUDY IMPLEMENTATION

3.1 STUDY DESIGN

3.1.1 *Overall Trial Design*

Patients with prostate cancer who have more than 15% risk of lymph node (as defined by the Partin tables) metastasis will be eligible for this study. The initial part of this trial (first 10 patients) explores the feasibility of using intensity modulated radiation therapy (IMRT) to deliver standard dose (4500 cGy) to the pelvic lymph nodes while dramatically reducing the volume of small bowel exposed. The prostate gland will receive the standard dose (7560 cGy). These first 10 patients will also undergo 3 to 5 CT simulations throughout the course of their therapy. On each simulation, the initial treatment plan will be re-run and the dose-volume data from target and normal tissues will then be re-analyzed. From this analysis we will be better able to determine the size of margins needed to account for organ motion and

changes such as varying amounts of gas in the bowel and fluid in the bladder. To the best of our knowledge, no such analyses have been published.

If the initial part of this trial is feasible, we will then proceed to a phase I dose escalation trial of radiation to the at-risk lymph nodes. The scientific objective is to determine what dose of external beam radiation is tolerable. Specifically, we will estimate the maximum tolerated dose (MTD) of external beam radiation to pelvic lymph nodes of interest in patients with prostate cancer.

Anatomic MRI and MR biological images will be obtained Tissue will be acquired from sites of interest, with biopsy locations precisely translated (co-registered) to an MR image of reference. Fiducial markers (gold seeds) may be left at the biopsy site(s) to direct future radiation therapy. The patient will undergo a standard CT simulation for radiation therapy treatment planning. The MR and CT images will be fused. Areas of image abnormality will undergo dose escalation as described below. The remainder of the prostate gland will receive standard dose (as per the Radiation Therapy Oncology Group (RTOG) 9406 study 7560 cGy in 180 cGy daily fractions.[1] Treatments will occur at the NCI, Department of Radiation Oncology on weekdays. There will be no treatments on weekends or holidays.

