3.1.2 Dose Escalation

The first 10 patients will receive 4500c Gy to the prostate and pelvic nodes, followed by IMRT to prostate alone to 7560 cGy, which is standard dose to less volume than during whole pelvis radiation therapy.

The primary objective of this study to determine the MTD of radiation to pelvic lymph nodes (LNs) of interest (as determined by MRI) in patients with prostate cancer. based on evaluating acute toxicity. The study will be conducted with a dose-escalation design with 3 patients in each dose cohort.

Cohort	Prescription Dose to Lymph Node Regions	Max Dose to > 10 cc of Small Bowel	Max Dose Allowed Beyond Prostate + 7 mm
I	5040 cGy	5500cGy	7560 cGy
II	5400 cGy	5500cGy	7560 cGy
III	5900 cGy	5500cGy	7560 cGy

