3.1.5 Definition of Maximum Tolerated Dose (MTD)

The primary objective is to estimate the MTD of external beam radiation that results in limiting acute toxicity. The MTD is defined as the dose level immediately below the dose level at which 2 or more in a cohort of either 3 or 6 patients experienced a DLT attributed to radiation therapy. If DLT does not occur at the highest dose level the protocol will be amended to escalate by 10% in cohorts of 3 patients each with the standard 3-6 dose escalation procedure.

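### Section 5.4 caps the trial at 19 patients, a maximum only without cohort expansion, but its escalation probabilities assume expansion, under which the maximum is 28

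*Combined protocol and SAP*

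**What the plan says.** The plan describes the phase I escalation rule in two ways.

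- **Précis, Design.** Three patients per cohort and no expansion: "If fewer than 2 of 3 patients experience an acute DLT than patients will be accrued to the next dose cohort". Two or more DLTs in 3 mean that the MTD has been exceeded.
- **Section 3.1.3.** Escalate after 0 of 3. After one DLT, expand: "If a DLT occurs in one of three patients then an additional 3 patients will be accrued to that dose level". Escalate from the expanded cohort only if fewer than 2 of 6 have a DLT.
- **Section 3.1.5.** This agrees with 3.1.3. The MTD is the level below the one at which "2 or more in a cohort of either 3 or 6 patients experienced a DLT attributed to radiation therapy".

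The table in Section 3.1.2 lists three cohorts (I to III) after the feasibility patients. Section 3.1.1 counts those patients as part of the same trial: "The initial part of this trial (first 10 patients) explores the feasibility".

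Section 5.4 then gives two figures: "the probabilities of dose escalation are 0.91, 0.49, 0.17, and 0.03 if the probabilities of a DLT are 0.1, 0.3, 0.5, and 0.7", and "The maximum number of patients accrued to this trial will be 19 patients". It expects to accrue these patients within 2 years.

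**The concern.** Both figures in 5.4 depend on the escalation rule, so both should follow from the same one. They do not. The cap has no room for a single expansion if all three levels open, yet the printed probabilities assume that expansion takes place.

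Two things are at stake. The first is the sample size. Under 3.1.3, 19 is exceeded if any level expands and level III opens, or if levels I and II both expand. A trial that reaches the cap must then amend accrual, stop before the escalation rule has run its course, or skip an expansion. Skipping one changes the printed operating characteristics at that level.

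The second is the decision rule itself. After 1 DLT in 3, the Précis escalates and 3.1.3 adds 3 patients at the same level. This is not a case of the summary leaving out detail, because the same result leads to a different action.

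**Working it through.** **Inputs.** Feasibility patients: 10 (3.1.1). Escalation cohorts: 3 (3.1.2). Base cohort: 3 (3.1.2). Expanded cohort: 6 (3.1.3, 3.1.5). Stated cap: 19; stated probabilities: 0.91, 0.49, 0.17, 0.03 at DLT risks p = 0.1, 0.3, 0.5, 0.7 (5.4). Write q = 1 − p.

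**Step 1: the printed probabilities.**

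- Précis rule: P(escalate) = q³ + 3pq².
- 3.1.3 rule: P(escalate) = q³ + 3pq² × q³, because after 1 of 3 the added 3 patients must all be free of DLT.

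| p | q³ | 3pq² | Précis rule | 3.1.3 rule | Printed |
|---|---|---|---|---|---|
| 0.1 | 0.729 | 0.243 | 0.972 | 0.906 | 0.91 |
| 0.3 | 0.343 | 0.441 | 0.784 | 0.494 | 0.49 |
| 0.5 | 0.125 | 0.375 | 0.500 | 0.172 | 0.17 |
| 0.7 | 0.027 | 0.189 | 0.216 | 0.032 | 0.03 |

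All four printed values are the 3.1.3 results after rounding. None matches the Précis rule. Three other variants also fail to match all four: escalating on 0 of 3 only, a fixed cohort of 6 with fewer than 2 DLTs, and 1 of 3 followed by at most 1 of the added 3.

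**Step 2: the cap.**

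- No expansion: 10 + 3 × 3 = 19, as printed.
- With expansion: 10 + 3 × 6 = 28, which is 9 more.

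Reading 19 as phase I only does not help. The phase I maximum is 9 without expansion and 18 with it, and 5.4 refers to accrual to the trial.

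**Step 3: how often 3.1.3 needs more than 19.** Write a = q³, e = 3pq², s = 1 − a − e. For p = 0.1 at every level, s = 0.028, and:

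- P(N = 13) = s = 0.028
- P(N = 16) = e(1 − a) + as = 0.0659 + 0.0204 = 0.0863
- P(N = 19) = a²(1 − e) + eas + ae(1 − a) = 0.4023 + 0.0050 + 0.0480 = 0.4553
- P(N > 19) = 1 − 0.5695 = 0.430

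The same enumeration for other assumed risks gives:

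| DLT risk at levels I/II/III (assumed) | P(N > 19) | Expected N | Mean excess over 19 |
|---|---|---|---|
| 5% throughout | 0.31 | 19.95 | 1.07 |
| 10% throughout | 0.43 | 20.17 | 1.60 |
| 20% throughout | 0.38 | 19.18 | 1.52 |
| 30% throughout | 0.22 | 17.52 | 0.90 |
| 50% throughout | 0.035 | 14.96 | 0.13 |
| 70% throughout | 0.001 | 13.69 | 0.00 |
| 5/10/20% | 0.50 | 20.70 | 1.87 |
| 10/15/25% | 0.50 | 20.48 | 1.98 |
| 10/20/30% | 0.47 | 20.27 | 1.86 |
| 10/30/50% | 0.34 | 19.49 | 1.33 |

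All 28 are needed with probability (ea)₁ × (ea)₂ × e₃, where the subscript is the level. This is at most 0.0154 in these scenarios (10/20/30%).

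**Step 4: how far the two rules differ.** The result on which they conflict, 1 DLT in 3, has probability 0.243 per cohort at p = 0.1 and 0.441 at p = 0.3. At an assumed 30% risk throughout, all three levels are cleared with probability 0.784³ = 0.48 under the Précis rule and 0.494³ = 0.12 under 3.1.3.

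**The case against.** The arithmetic is not in dispute, and no passage reconciles the figures. The best counter-case concerns weight.

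- **19 may be a mislabelled base case.** Sections 3.1.2 and 3.1.3 both start from 3 patients per cohort, so 19 is also the count under 3.1.3 when all three levels open and none expands. The plan does not derive 19, so its origin is inference. This stands, but the sentence says maximum, and under 3.1.3 that is wrong.
- **The body outweighs the summary.** Sections 3.1.3, 3.1.5 and all four probabilities agree; only the Précis states a different rule. This is fair as to the balance of the text. No order of precedence is given, however, and if the body governs, the cap is the error.
- **Ending without an MTD is not peculiar to the cap.** Under 3.1.5 an MTD needs some level with at least 2 DLTs. At an assumed 10% risk throughout, an uncapped 3.1.3 trial clears all three levels with probability 0.906³ = 0.74. This stands, so the effect of the cap must be reported separately.
- **The overrun is small.** The mean excess is about 2 patients at most, and a cap set too low does not by itself expose anyone to a higher dose. This limits the sample-size consequence but does not touch the conflict over what follows 1 DLT in 3.
- **Amendment is already foreseen.** Section 3.1.5 foresees it only for levels above the highest planned dose, not for expansions within the three listed.

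**Conclusion.** The concern holds. No single rule in the document yields both figures in 5.4. The probabilities are those of 3.1.3 and 3.1.5, for which the maximum is 28. The cap of 19 is a maximum only without expansion, as in the Précis. These statements are exact and need no assumption beyond the three listed levels.

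How often the cap would bind depends on DLT risks that the plan does not give. In the scenarios at 5% to 30%, constant or rising, the probability is 0.22 to 0.50; it is 0.34 for 10/30/50%, and negligible at 70% throughout. The expected total across all scenarios is 13.7 to 20.7.

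This must be corrected, because it concerns the phase I decision rule, its operating characteristics and the sample size together. The review takes no position on which escalation rule is right.

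**What to change.** Reconcile the Précis with 3.1.3 and 3.1.5 first, then make 5.4 follow the rule that is kept.

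- **If 3.1.3 and 3.1.5 stand:** correct the Précis, keep the probabilities, and state a maximum of 28 (10 plus up to 18). Give the expected total under stated DLT assumptions. Revisit the 2-year forecast: 19 in 2 years implies 9.5 a year, at which 28 would take 28 / 9.5 = 2.9 years.
- **If the Précis rule stands:** correct 3.1.3 and 3.1.5, keep 19, and restate the probabilities as 0.97, 0.78, 0.50 and 0.22.
- **If 19 is a hard limit alongside 3.1.3:** say so, and say what happens when it is reached. Give the probability that the cap stops escalation early, separately from the probability that all levels are cleared and no MTD is defined.

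Under either rule, say that levels added by amendment under 3.1.5 come on top of the stated maximum. Also correct the cross-reference in 5.4: it points to 3.1.1, but the cohorts are in 3.1.2 and the MTD is defined in 3.1.5. If accrual is already complete, which the document does not say, the report should state which rule was applied.

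The cost is a few sentences and an IRB amendment. Keeping the expansion rule adds about 2 patients on average at most in these scenarios and makes the stated maximum and duration less favourable. Keeping the Précis rule makes the printed escalation probabilities less reassuring.
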